7. PHARMACOKINETIC ANALYSIS (EXPLORATORY)

7.1 Measurements and Collection Schedule

All concentration data will be included in the calculation of the individual PK parameters, the individual concentration-time plots (based on actual sample times), and in the mean concentration-time plots (based on nominal sample times). However, if there are any significant deviations from nominal sample times, some concentration data may be excluded from mean concentration-time plots and/or additional concentration-time plots of the mean data may be provided. All deviations and excluded data will be provided and discussed in the CSR.

7.2 Bioanalytical Method

Plasma sample analysis for S 48168 (ARM210) will be performed by Nuvisan Pharma Services (Germany) using validated procedures and methods.

7.3 Investigational Product and PK Analyte Information

S 48168 (ARM210) can be described as follows. S 48168 (ARM210) in the hemifumarate salt formulation has an empirical formula $C_{18}H_{18}NO_3S \cdot C_2H_2O_2$ and a molecular weight of 387.42 g/mol. The free base has a molecular weight of 329.42 g/mol.

7.4 Pharmacokinetic Concentrations

Serial blood samples for the determination of plasma S 48168 (ARM210) will be collected at predose and 0.5, 1, 2, 3, 4, 5, 6, 8, 12, and 24 hours postdose on Days 1 and 28. A predose sample will also be collected on Day 14.

7.5 Noncompartmental Pharmacokinetic Analysis and Parameter Calculation

7.5.1 Plasma Pharmacokinetic Parameters

The appropriate noncompartmental PK parameters will be calculated from the plasma S 48168 (ARM210) concentration-time data using Phoenix® WinNonlin® Version 7.0 or higher sample times will be used in the calculations of the PK parameters. The calculation of the actual time for S 48168 (ARM210) will be in respect to the start of dose administration time of S 48168 (ARM210) on every PK day. All PK parameters included in the protocol are listed in Table 6.1 below, and are defined as appropriate for study design.

Table 6.1. Noncompartmental Pharmacokinetic Parameters to be Calculated (Day 1)

Parameter	Definition	Method of Determination
AUC0-24	Area under the concentration-time curve from time 0 to the 24 hours postdose	Calculated using the Linear Trapezoidal with Linear Interpolation Method. If a value could not be obtained at 24 hours the parameter will be set to missing
AUC0-t	Area under the concentration-time curve from time 0 to the time of the last observed/measured non-zero concentration	Calculated using the Linear Trapezoidal with Linear Interpolation Method
AUC0-inf	Area under the concentration-time curve from time 0 extrapolated to infinity	$AUC0\text{-inf} = AUC0\text{-t} + (Clast/kel)$ where Clast is the last observed/measured concentration
AUC%extrap	Percent of AUC0-inf extrapolated	Calculated as $(1 - AUC0\text{-t}/AUC0\text{-inf}) * 100$
Cmax	The maximum observed concentration	Taken directly from bioanalytical data
Tmax	The time to reach Cmax	Taken from clinical database as the difference in the time of administration and the time of the blood draw which is associated with the Cmax.
Kel	Apparent first-order terminal elimination rate constant calculated from a semi-log plot of the plasma concentration versus time curve.	The parameter will be calculated by linear least-squares regression analysis using the maximum number of points in the terminal log-linear phase (e.g., three or more non-zero plasma concentrations).
t½:	Apparent first-order terminal elimination half-life	Calculated as $0.693/Kel$

Parameter	Definition	Method of Determination
Tlag	Lag time – the time delay between drug administration and the onset of absorption; where onset of absorption	Calculated as the time point prior to the first observed/measured non-zero plasma concentration

Table 6.2. Noncompartmental Pharmacokinetic Parameters to be Calculated (Day 28)

Parameter	Definition	Method of Determination
AUC0-tau	The area under the concentration versus time curve from the start of drug infusion over the final dosing interval (tau)	Calculated using the linear trapezoidal method with linear interpolation. Tau is equal to 24 hours.
Cmax,ss	The maximum observed concentration at steady state	Taken directly from bioanalytical data
Tmax,ss	The time of the maximum observed concentration at steady state	Taken directly from bioanalytical data. Tmax,ss is the first time point if Cmax,ss occurs at 2 time points
Cmin	Minimum observed concentration at the end of the dosing interval	Taken directly from bioanalytical data
Tmin	Time to reach Cmin	Taken directly from bioanalytical data. Tmin is the first time point if Cmin occurs at 2 time points
RA(AUC)	Accumulation ratio for AUC (steady state versus single dose)	Calculated as AUCtau Day 28/AUC0-24 Day 1
RA(Cmax)	Accumulation ratio for Cmax (steady state versus single dose)	Calculated as Cmax Day 28/Cmax Day 1.
Ctrough_D13	Day 13 Ctrough	Taken directly from bioanalytical data. Day 13 Ctrough is the predose of Day 14

Pharmacokinetic parameters will not be calculated for subjects with less than 2 consecutive postdose time points with quantifiable concentrations. Subjects for whom there are insufficient data to calculate the PK parameters will be included in the concentration tables only and excluded from the descriptive statistics.

Concentrations will be presented in the report at the same precision as received from the bioanalytical laboratory. Concentrations below the lower limit of quantification (LLOQ) will be assigned a value of zero if they occur between time zero (predose) and the first measurable plasma concentration after the first dose and missing thereafter, and will be treated as such for the purpose of calculating PK parameters and summary statistics.

The Kel will be determined using linear regressions composed of least 3 data points. The Kel will not be assigned if 1) the terminal elimination phase is not apparent, 2) if Tmax is one of the 3 last data points, or 3) if the R^2 value is less than 0.8. In cases where the Kel interval is not assigned, the values of $t_{1/2}$, AUC0-inf and AUC%extrap are considered not calculable and will not be reported. Wherever the resulting $t_{1/2}$ is

more than half as long as the sampling interval, the K_{el} values and associated parameters ($t^{1/2}$, AUC_{0-inf} and AUC%extrap) may not be presented as judged appropriate and in accordance with Celerion SOPs.

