10.2 Study Endpoints

Primary endpoint:

Composite safety and tolerability profile

(Frequencies of the following: TEAEs \geq grade 2 in severity (CTCAE version 5), all SAEs, and all AESIs).

Exploratory Endpoints:

S 48168 (ARM210) pharmacokinetics

Day 1 composite PK profile (for study drug naïve participants only)

(Comprised of the following: AUC0-t, AUC0-inf, Cmax, Tmax, and t_{1/2}).

Day 28 (not to exceed Day 30) composite PK profile

(Comprised of the following: AU_{tau}, Cmax, Tmax, Cmin, RAAUC, and RACmax).

S 48168 (ARM210) pharmacodynamics

RyR1-calstabin1 binding

(Change from baseline in RyR1-calstabin1 binding (arbitrary units)).

RyR1 channel integrity

(Change from baseline in RyR1-mediated Ca²⁺ leak (arbitrary units)).

Muscle/motor function and fatigue

Hand grip strength (kg), pinch strength (kg).

Time taken to complete each of the following (seconds): walk 10-meters, supine to stand, ascend 4 stairs, and descend 4 stairs.

MFM-32 score for domains 1, 2, 3, and total (% of maximum score).

PROMIS-fatigue subscale score (t-score).

Quantitative muscle strength (kg)

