No value for Kel, AUC_{0-inf}, AUC%extrap, or t_{1/2} will be reported for cases that do not exhibit a terminal log-linear phase in the concentration-time profile.

No PK parameters will be calculated for subjects with 2 or fewer consecutive time points with detectable concentrations.

Individual and mean plasma concentration time curves (both linear and log-linear) will be included in the final report.

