13.2 Statistical Methods

Detailed methodology for summary and statistical analyses of the data collected in this study will be documented in a Statistical Analysis Plan (SAP) (Appendix # 18). The SAP will be prepared by Celerion and agreed upon with the Sponsor. This document may modify the plans outlined in the protocol; however, any major modifications of the primary endpoint definition and/or its analysis will also be reflected in a protocol amendment. Additional statistical analyses other than those described in this section may be performed if deemed appropriate.

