2.2 Endpoints

Primary:

Composite safety and tolerability profile

(Frequencies of the following: TEAEs \geq grade 2 in severity (CTCAE version 5), all SAEs, and all AESIs).

Methods: Safety and tolerability of S 48168 (ARM210) will be determined by monitoring Adverse Events (AEs) over 28 days of treatment via patient interviews, patient diary reviews, physical examinations, echocardiograms, electrocardiograms (ECGs), vital signs, and laboratory safety tests. A reference dataset of AEs/SAEs obtained from a natural history study of RYR1-RM will also be available to assist in interpretation of safety events. The Columbia-Suicide Severity Rating Scale (C-SSRS) will also be administered pre- and post-intervention. The frequency and severity of clinically significant AEs will be compared between treatment and historical controls including a previously conducted natural history study at the NIH.

Exploratory:

1. To determine PK of a 28-day administration of S 48168 (ARM210) in RYR1-RM affected individuals.

Endpoints:

Day 1: AUC_{0 t}, AUC_{0 inf}, C_{max}, T_{max}, and t_{1/2}

Day 28: AUC_{tau}, C_{max}, T_{max}, C_{min}, RAAUC, and RAC_{max}

Secondary PK parameters will include: AUC₀₋₂₄, AUC%extrap, T_{min}, K_{el}, T_{lag}, and Day 13 C_{trough} (associated with Day 14 pre-dose). Additional parameters may be calculated as appropriate.

Methods: Bloods for PK assessments will be drawn at baseline (Day 0, 24h PK), at the study mid-point (day 14 \pm 2 days, trough PK), and at the final study visit (Day 28, 24h PK). Whole blood will be processed, and the plasma fraction stored for batch PK analyses.

2. To explore if S 48168 (ARM210) treatment increases RyR1-calstabin1 binding in skeletal muscle of RYR1-RM affected individuals.

Endpoint: Change from baseline in relative RyR1-calstabin1 binding (AU) and (pending sufficient tissue yield) change from baseline in relative Fluo-4 signal (AU).

Methods: Skeletal muscle tissue will be obtained from participants pre- and post-intervention by needle biopsy. This tissue will be assessed for RyR1-calstabin1

binding by co-immunoprecipitation followed by protein detection. The percentage of Calstabin1 binding to RyR1 pre-dose will be compared to the percentage obtained post-dose in each patient. Pending sufficient tissue yield, muscle membrane preparations may be assessed for changes in calcium permeability (Fluo-4 signal) using a thapsigargin assay.

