9. SUMMARY OF CHANGES FROM PROTOCOL-PLANNED ANALYSIS

The analyses described in this SAP are aligned with those analyses described in the protocol.

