Plasma S 48168 (ARM210) Pharmacokinetic Parameters Following Single Oral Administration of 120 mg S 48168 (ARM210) (6 x 20 mg Tablets) for 28 Days (Patients) (Treatment A) (Day 1) (Pharmacokinetic Population)

Subject Number	Treatment Sequence	Study Period	Parameters					
			Param1 (units)	Param2 (units)	Param3 (units)	Param4 (units)	Param5 (units)	Param6 (units)
X	XXXX	X	XXXX	X.XX	XXX	XXXX	XX.X	X.XXXX
X	XXXX	X	XXXX	X.XX	XXX	XXXX	XX.X	X.XXXX
X	XXXX	X	XXXX	X.XX	XXX	XXXX	XX.X	X.XXXX
X	XXXX	X	XXXX	X.XX	XXX	XXXX	XX.X	X.XXXX
X	XXXX	X	XXXX	X.XX	XXX	XXXX	XX.X	X.XXXX
X	XXXX	X	XXXX	X.XX	XXX	XXXX	XX.X	X.XXXX
X	XXXX	X	XXXX	X.XX	XXX	XXXX	XX.X	X.XXXX
X	XXXX	X	XXXX	X.XX	XXX	XXXX	XX.X	X.XXXX
X	XXXX	X	XXXX	X.XX	XXX	XXXX	XX.X	X.XXXX
X	XXXX	X	XXXX	X.XX	XXX	XXXX	XX.X	X.XXXX
X	XXXX	X	XXXX	X.XX	XXX	XXXX	XX.X	X.XXXX
X	XXXX	X	XXXX	X.XX	XXX	XXXX	XX.X	X.XXXX
X	XXXX	X	XXXX	X.XX	XXX	XXXX	XX.X	X.XXXX
X	XXXX	X	XXXX	X.XX	XXX	XXXX	XX.X	X.XXXX
X	XXXX	X	XXXX	X.XX	XXX	XXXX	XX.X	X.XXXX
X	XXXX	X	XXXX	X.XX	XXX	XXXX	XX.X	X.XXXX
n			XX	XX	XX	XX	XX	XX
Mean			XXXX.X	X.XX	XXXX.X	XXXX.X	XX.XX	X.XXXX
SD			XX.XXX	X.XXX	XX.XXX	XX.XXX	XX.XX	X.XXXX
CV%			XX.X	XX.X	XX.X	XX.X	XX.X	XX.X
SEM			XX.XXX	X.XX	XX.XXX	XX.XXX	XX.XX	X.XXXX
Minimum			XXX	X.XX	XXX	XXX	XX.X	X.XXX
Median			XXXX.X	X.XX	XXXX.X	XXXX.X	XX.XX	X.XXXX
Maximum			XXX	X.XX	XXX	XXX	XX.X	X.XXX
Geom Mean			XXXX.X	XXXX.X	XXXX.X	XXXX.X	XXXX.X	XXXX.X
Geom CV%			XX.X	XX.X	XX.X	XX.X	XX.X	XX.X

. = Value missing or not reportable.

Notes for Generating the Actual Table:

Presentation of Data:

- Template to be used CPPar1.
- PK Parameters will be presented in the following order and with following units: Day 1: AUC0-t <unit>, AUC0-inf <unit>, AUC%extrap <unit>, Cmax <unit>, Tmax <unit>, Kel <unit>, t½ <unit>, and Tlag <unit>. Day 28: AUC0-tau <unit>, Cmax,ss <unit>, Tmax,ss <unit>, Cmin <unit>, Tmin <unit>, RA(AUC) <unit>, RA(Cmax) <unit>, and Cthrough_D13 <unit>
- n will be presented as an integer (with no decimal);
- Parameter values for exposure based parameters (i.e. AUCs, Cmax) will be presented with, at maximum, the precision of the bio data, and, at minimum, 3 significant figures (to be determined by the PKist once bio data are received). Summary statistics for exposure parameters will be presented as: Mean, Median, and Geom Mean+1; SD and SEM +2, Min and Max +0.

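### The SAP sets a lower sample minimum for PK parameters than the protocol, and its Day 1 tables omit AUC0-24, so an incomplete Day 1 profile could bias the tabulated AUC0-t low

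*SAP*

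**What the plan says.** **Minimum number of samples.** Protocol 13.1: "No PK parameters will be calculated for subjects with 2 or fewer consecutive time points with detectable concentrations". SAP 7.5.1: "Pharmacokinetic parameters will not be calculated for subjects with less than 2 consecutive postdose time points with quantifiable concentrations". SAP 9 declares no difference: "The analyses described in this SAP are aligned with those analyses described in the protocol". Protocol 13.2 would have permitted one, since it says of the SAP: "This document may modify the plans outlined in the protocol".

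**Which Day 1 AUC is tabulated.** Protocol 10.2 defines the Day 1 PK endpoint as "Comprised of the following: AUC0-t, AUC0-inf, Cmax, Tmax", plus half-life. SAP 2.2 places AUC0-24 in the second tier: "Secondary PK parameters will include: AUC₀₋₂₄" and others. The SAP shells (11.1 for Tables 11-2 and 11-3, 11.2 for the Section 14 tables) begin the parameter list with "Day 1: AUC0-t <unit>, AUC0-inf <unit>, AUC%extrap <unit>, Cmax <unit>". AUC0-24 does not appear in it.

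**Completeness.** In SAP Table 6.1 the rule for AUC0-24 is: "If a value could not be obtained at 24 hours the parameter will be set to missing". AUC0-t runs to the last measurable concentration, whenever that falls. Under SAP 7.5.1, half-life and AUC0-inf may be left out when the half-life is more than half the sampling interval.

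**Who is summarized.** Both documents limit the PK population to participants with an evaluable profile and cite availability of measurements as an example. Neither gives a minimum sample count or a required last time.

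**The concern.** Taken literally, a Day 1 profile with exactly two consecutive quantifiable samples is analysed under the SAP and not under the protocol. Programmers work from the SAP, and a reader of SAP 9 would not know that the rule had changed.

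The second gap is independent of the first. Table 11-2 sets patients beside healthy volunteers, with AUCs as geometric means. An AUC0-t covering 2 h or 4 h would enter the same mean as values covering 24 h, and would count as very low exposure rather than as missing information. AUC0-24 guards against this but is not in the table. AUC0-inf may be absent too: Protocol 9.4 gives a half-life of 20 h, which exceeds 12 h, half of the 24 h sampling interval. AUC0-t could then be the only Day 1 AUC shown. At stake is the reliability of a small, exploratory comparison.

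**Working it through.** **Inputs from the documents**
- Half-life 20 h, median Tmax 3–3.5 h, accumulation ratio about 1.5–1.8 (Protocol 9.4).
- Linear trapezoidal rule (SAP Table 6.1); geometric mean for AUCs (SAP 11.1).
- Sampling at 11 times in SAP 7.4. The current protocol flow chart has 8, read as 0, 1, 2, 4, 6, 8, 12 and 24 h.
- Three participants dosed at each level so far, and about 8–20 completers planned (Protocol 11.1). Subtracting the three at 120 mg leaves about 5–17 at 200 mg. Re-enrolled participants have no Day 1 profile.

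**Assumptions**
- One-compartment oral profile.
- Absorption lag 0.5–1.5 h. The protocol mentions a lag but gives no figure.
- All other profiles in the group are complete and of equal exposure.

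**Step 1: check the model against the plan's own figure.** With k = ln 2 / 20 = 0.0347 per hour, the accumulation ratio is 1/(1 − exp(−24k)) = 1.77. This lies within the stated 1.5–1.8.

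**Step 2: profile.** After the lag, C(t) is proportional to exp(−k(t − lag)) − exp(−ka(t − lag)). The absorption rate ka solves ln(ka/k)/(ka − k) = Tmax − lag. With lag 1 h and Tmax 3 h, ka = 2.08.

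**Step 3: fraction captured.** r = truncated AUC0-t / full AUC0-24, both by linear trapezoid on the same grid. In the Step 2 example on the 8-time grid, the first two quantifiable samples fall at 2 h and 4 h, and r = 0.142.

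**Step 4: effect on the geometric mean.** One truncated profile among n changes it by r^(1/n) − 1. For r = 0.142:
- n=3: 0.522 − 1 = −48%
- n=8: 0.783 − 1 = −22%

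Ranges over both grids, Tmax 3–3.5 h and lag 0.5–1.5 h:

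| One incomplete Day 1 profile | r | n=3 | n=5 | n=8 | n=17 |
|---|---|---|---|---|---|
| Two quantifiable samples, last at 2–4 h | 0.05–0.14 | −48 to −64% | −32 to −46% | −22 to −32% | −11 to −16% |
| Three quantifiable samples, last at 3–6 h | 0.10–0.26 | −37 to −53% | −24 to −37% | −16 to −25% | −8 to −13% |
| Only the 24 h sample missing | 0.54–0.57 | −17 to −18% | about −11% | about −7% | about −3% |

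**Step 5: what each correction achieves.** Restoring the protocol minimum removes the first row only. The second and third rows satisfy the protocol rule and remain. With AUC0-24, all three profiles become missing: the bias is zero and n falls by one.

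**Step 6: Cmax.** In the worst case (lag 0.5 h, Tmax 3.5 h, last sample at 2 h) the truncated participant's Cmax is 0.905 of the full value. At n=8 that moves the geometric mean by 0.905^(1/8) − 1, about −1%. With a last sample at 3 h or later, the individual Cmax is within 1% of the full value.

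**The case against.** Several points on the other side have force.

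- **AUC0-t is the protocol's own Day 1 endpoint.** A reader might infer that tabulating it departs from the protocol. It does not. The gap is the absence of AUC0-24 beside it.
- **The PK population may already exclude such a profile.** One that stops at 2–4 h is an obvious candidate, and excluded participants are listed but not summarized (SAP 7.6). This stands as a possible safeguard. It depends on judgement, because the only general numeric rule in the SAP is the two-sample one.
- **The situation may be rare.** Day 1 draws are taken in the clinic and Protocol 12 calls them critical. A participant withdrawn early would probably fail the 80% compliance standard in Protocol 11.8.1. The documents give no frequency.
- **The two rules count differently.** The protocol counts time points and the SAP counts post-dose ones. On Day 28 a detectable predose sample plus two post-dose samples satisfies both, so the conflict bites mainly on Day 1.
- **The outlier would be visible.** The tables list every participant. At n=8, one value at 0.058–0.138 among seven equal values gives a geometric CV of sqrt(exp((ln r)²/8) − 1), about 132% to 80%. Protocol 12.10.3 cites about 15%.
- **Little hangs on Day 1.** The exposure hypothesis concerns steady state, and SAP 7.7 makes the comparison descriptive. Protocol 12.10.3 treats a fall of about 50% as clinically meaningful, and the n=8 figures do not reach that.

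These limit the consequence. They do not remove the contradiction between the two rules, the incorrect statement in SAP 9, or the missing table row.

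**Conclusion.** Two defects are confirmed from the text. The sample minimum differs between Protocol 13.1 and SAP 7.5.1 while SAP 9 reports alignment. The Day 1 tables also omit the one AUC that is set to missing without a 24 h sample.

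A reader might infer that the lower SAP minimum by itself produces a fall of some fixed size, such as 20–30%. The documents do not support that. A fall of that order needs a two-sample early cut in a group of about 8. Across the cases worked, the effect runs from about 3% (24 h sample missing, n=17) to about 64% (two samples, n=3), and most of it survives under the protocol's own minimum. The main driver is AUC0-t without a completeness condition. Nor do the figures support a claim that Cmax would be materially understated, or that the steady-state comparison is affected.

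The sizes rest on the one-compartment shape, the assumed lag, and one incomplete profile being kept among otherwise complete and equal ones. The importance is minor: exploratory, descriptive and of unknown frequency, but easily corrected.

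**What to change.** 1. In SAP 7.5.1, restore the protocol rule: no parameters with 2 or fewer consecutive quantifiable time points. If the lower minimum is intended, declare and justify it in SAP 9.
2. Add AUC0-24 to the Day 1 parameter lists for Tables 11-2 and 14.2.1.5, .7, .9 and .11, and name it as the Day 1 exposure measure for comparing patients with volunteers.
3. Keep AUC0-t as the protocol endpoint, and flag any value whose last sample is before 24 h. Restricting its summary to 24 h profiles is optional once AUC0-24 is shown.

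The cost is a sentence or two and one table row; AUC0-24 is already calculated for the accumulation ratio. The downside is that a participant without a 24 h sample drops out of the AUC0-24 summary, which matters in groups this small, but that participant stays in the listing.

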7.6 Data Summarization and Presentation

All S 48168 (ARM210) PK concentration and PK parameter descriptive statistics will be generated using WinNonlin® Version 7.0 or higher and/or SAS Version 9.4.

Summary statistics, including sample size (n), arithmetic mean (mean), standard deviation (SD), coefficient of variation (CV%), standard error of the mean (SEM), median, minimum, and maximum will be calculated for all nominal concentration time points. The plasma concentrations of S 48168 (ARM210) will be calculated by nominal time. Excluded subjects due to major protocol deviations will be included in the concentration table listing, but will be excluded from the summary statistics and noted as such in the tables. All BLQ values will be presented as “BLQ” in the concentration table listing and footnoted accordingly.

The level of precision for each statistic will be presented as follows: mean, median, minimum, maximum, SEM, and SD in same precision as in bioanalytical data, n will be presented as an integer, and CV% will be presented to 1 decimal place.

Summary statistics (n, mean, SD, CV%, SEM, median, minimum, and maximum, geometric means, and geometric CV%) will be calculated for plasma S 48168 (ARM210) PK parameters. Excluded subjects will be included in the PK parameter table listing, but will be excluded from the summary statistics and noted as such in the tables. PK parameters will be tabulated by dose level and listed by subject and parameter.

Mean and individual concentration-time profiles will be presented on linear and semi-log scales. Linear mean plots will be presented with and without SD.

7.7 Statistical Analysis of PK Parameters

All data will be summarized and compared descriptively with no formal statistical analysis performed in this study.

